10.4 Dispensing and Preparation

The unblinded DC products (pp65 DC vaccines) will be delivered from the MPACT facility directly to the clinic under the supervision of the trained research staff. Each labeled patient vaccine will be transported to the clinic in a separate cooler. DCs will be administered according to protocol. The patient’s name, Study ID, DOB, and Duke history number will be double verified prior to DC administration as is standard Duke transfusion procedure.

The radiolabeled DC products used with the migration studies within Groups I and II will be prepared from the pp65 DC vaccines sent from the MPACT facility to the Radiopharmacy and dispensed radiolabeled from the Duke Radiopharmacy.

Please see Section 9.1.7 for blinding, preparing and dispensing the pre-conditioning study drugs (i.e., saline, Td, and unpulsed DCs).

Patients in Group III will receive basiliximab from the Duke ICS Pharmacy.

Table 3. Dispensing of Study Agents

MPACT Facility	Duke ICS Pharmacy	Duke Radiopharmacy
CMV pp65-LAMP mRNA-pulsed DCs	Td used for booster and for pre-conditioning (blinded for Groups I and II only)	CMV pp65-LAMP mRNA loaded mature DCs labeled with ¹¹¹ In
	Saline used for pre-conditioning (blinded)	
	Unpulsed DCs for pre-conditioning (blinded)	
	Basiliximab	

10.5 Compliance and Accountability

All DC vaccines will be stored in the BTIP in a temperature controlled, locked access controlled storage unit. A drug log sheet will be used to track and document the drug. The products will be signed out and distributed by the BTIP laboratory manager. The Duke BTIP personnel use safe medication practices to reduce the risk of medication errors and adverse events when setting up study drug procedures. Investigational drugs are ordered, received, stored, and dispensed for BTIP protocols that are approved by the DUHS IRB. Investigational drugs are stored separately from other drugs in an area of limited access and in accordance with special storage requirements. They are clearly labeled with the identity of the study drug and other control numbers. All drug transfers, receipts, and disposal are recorded in the Duke Nautilus system.

10.6 Disposal and Destruction

Radioactively labeled drug will be disposed of according to standard Duke radiation safety practices. Un-labeled drug will be autoclaved.

11 SUBJECT ELIGIBILITY

Inclusion Criteria

- Age \geq 18 years of age.
- WHO Grade IV Glioma with definitive resection prior to consent, with residual radiographic contrast enhancing disease on the post-operative CT or MRI of $<$ 1 cm in maximal diameter in any axial plane.
- MRI post RT does not show progressive disease at time of randomization
- Karnofsky Performance Status (KPS) of $>$ 80%.
- Hemoglobin \geq 9.0 g/dl, ANC \geq 1,500 cells/ μ l, platelets \geq 125,000 cells/ μ l.
- Serum creatinine \leq 1.5 mg/dl, serum SGOT and bilirubin \leq 1.5 times upper limit of normal.
- Signed informed consent approved by the Institutional Review Board.
- Female patients must not be pregnant or breast-feeding. Female patients of childbearing potential (defined as $<$ 2 years after last menstruation or not surgically sterile) must use a highly effective contraceptive method (allowed methods of birth control, [i.e. with a failure rate of $<$ 1% per year] are implants, injectables, combined oral contraceptives, intra-uterine device [IUD; only hormonal], sexual abstinence or vasectomized partner) during the trial

and for a period of > 6 months following the last administration of trial drug(s). Female patients with an intact uterus (unless amenorrhea for the last 24 months) must have a negative serum pregnancy test within 48 hours prior to first study procedure (leukapheresis).

- Fertile male patients must agree to use a highly effective contraceptive method (allowed methods of birth control [i.e. with a failure rate of < 1% per year] include a female partner using implants, injectables, combined oral contraceptives, IUDs [only hormonal], sexual abstinence or prior vasectomy) during the trial and for a period of > 6 months following the last administration of trial drugs.

Exclusion Criteria:

- Pregnant or breast-feeding.
- Women of childbearing potential and men who are sexually active and not willing/able to use medically acceptable forms of contraception.
- Patients with known potentially anaphylactic allergic reactions to gadolinium-DTPA.
- Patients who cannot undergo MRI or SPECT due to obesity or to having certain metal in their bodies (specifically pacemakers, infusion pumps, metal aneurysm clips, metal prostheses, joints, rods, or plates).
- Patients with evidence of tumor in the brainstem, cerebellum, or spinal cord, radiological evidence of multifocal disease, or leptomeningeal disease.
- Severe, active comorbidity, including any of the following:
 - Unstable angina and/or congestive heart failure requiring hospitalization;
 - Transmural myocardial infarction within the last 6 months;
 - Acute bacterial or fungal infection requiring intravenous antibiotics at the time of study initiation;
 - Chronic obstructive pulmonary disease exacerbation or other respiratory illness requiring hospitalization or precluding study therapy;
 - Known hepatic insufficiency resulting in clinical jaundice and/or coagulation defects;
 - Known HIV and Hepatitis C positive status;
 - Major medical illnesses or psychiatric impairments that, in the investigator's opinion, will prevent administration or completion of protocol therapy;
 - Active connective tissue disorders, such as lupus or scleroderma that, in the opinion of the treating physician, may put the patient at high risk for radiation toxicity.
- Co-medication that may interfere with study results; e.g. immuno-suppressive agents other than corticosteroids.
- Prior, unrelated malignancy requiring current active treatment with the exception of cervical carcinoma in situ and adequately treated basal cell or squamous cell carcinoma of the skin. (Treatment with tamoxifen or aromatase inhibitors or other hormonal therapy that may be indicated in prevention of prior cancer disease recurrence, are not considered current active treatment.)
- Patients are not permitted to have had any other conventional therapeutic intervention other than steroids prior to enrollment outside of standard of care chemotherapy and radiation therapy. Patients who receive previous inguinal lymph node dissection, radiosurgery, brachytherapy, or radiolabeled monoclonal antibodies will be excluded.

- Current, recent (within 4 weeks of the administration of this study agent), or planned participation in an experimental drug study.
- Known history of autoimmune disease (with the exceptions of medically-controlled hypothyroidism and Type I Diabetes Mellitus).

12 SCREENING AND ON-STUDY TESTS AND PROCEDURES

12.1 Screening Examination

The screening examination will take place at the Duke PRTBTC clinic visit. An informed consent must be signed by the patient before any screening procedure takes place. The baseline physical and neurologic examination with KPS score along with standard of care blood work will be performed and documented by the neuro-oncology team and verified by the study team during this PRTBTC clinic visit. All subject data is standard of care evaluation that occurs for all patients being seen in the PRTBTC. If the subject is considered a screen failure prior to vaccine treatment, the source documents for electronic data entry will be obtained from the Duke electronic medical record.

CMP and CBC with auto differential are drawn at clinic visits and prior to surgical procedures per standard of care. A *CMV* immune screen will also need to be drawn at one of these clinic visits following consent and prior to initiation of vaccine therapy.

Initial clinical evaluations will also include a baseline MMSE testing. A baseline and study eligibility MRI (with and without gadolinium enhancement) of the brain per standard of care for comparison to subsequent MRI images will also be obtained.

The patient must have had a definitive resection. Residual radiographic contrast enhancement on post-resection CT or MRI must not exceed 1 cm in diameter in any axial planes at time of consent. Patients with progressive disease after radiation will not be a candidate for the vaccine despite being previously consented and will be removed from the study and replaced (please see Section 12.7.4 for radiologic evaluations).

During collection of tumor sample at resection at Duke University, primary tissue will be banked and stored for IHC assays. Tissue will be stored in formalin-fixed blocks for subsequent partitioning of pathology slides. For initial resection at Duke, slides will be sent for MGMT promotor methylation status and IDH-1/2 mutation analysis as part of the routine molecular diagnostic assay performed at Duke. If the surgery is performed outside of Duke and if such institutions do not incorporate these initial molecular diagnostic assays, slides from surgical blocks will be ordered for subsequent MGMT promoter methylation status and IDH-1/2 mutation analysis, so as to ensure baseline molecular diagnostics of the tumor for each patient. At the discretion of the study investigator, for surgical blocks containing initial resection and biopsy at recurrence (if applicable) tissue, formalin-fixed paraffin-embedded slides will be requested for immunohistochemistry assays for the detection of CMV. These slides for CMV detection will not exceed 10% of the original specimen block, so as to preserve adequate tissue should patients prefer future diagnostic studies. Patient consent will be obtained for obtaining these slides in either scenario if a surgery/biopsy was performed at Duke University or at an external institution.

If resection is done outside of Duke University Hospital, formalin-fixed paraffin-embedded slides sectioned from outside blocks, not to exceed 10% of surgical specimen block tissue, prepared on Fischer Plus glass or Histostix coated slides when available will be mailed to:

[name]
Duke Brain Tumor Immunotherapy Program
Department of Neurosurgery
The Preston Robert Tisch Brain Tumor Center at Duke
[name]
[name]
Duke University Medical Center
[name]

After patients have been consented, they will be entered into the Velos eResearch system.

12.2 Treatment Period

All enrolled patients will then undergo a leukapheresis for generation of DCs and for baseline immunological monitoring. Within 48 hours of leukapheresis, patients will have blood samples taken for the following tests as required by the Duke Apheresis Center: CBC, CMP, ionized Calcium, and β -HCG (for females of child-bearing potential). Total estimated blood volume required for these evaluations is 12-15 mLs. For patients without sufficient venous access for leukapheresis, a temporary central intravenous catheter may be inserted. To prevent the development of hypocalcemia from the citrate used for leukapheresis, all patients will be instructed to take oral Tums, 2 tablets three times a day and at bedtime the day before and the day of the leukapheresis procedure. Patients who have lower levels of calcium will be treated per Apheresis lab standard protocols under the direction of apheresis attending physician. This first leukapheresis will be approximately a 4-hour leukapheresis, and it is estimated that 10-12 L of blood will be processed during this leukapheresis. One red top tube will be obtained prior to each leukapheresis for immune monitoring (approximately 4 mLs).

Table 4. Schedule of Events

Appointment	Time and Range	Tumor Pathology ¹	Physical and Neurologic Exam KPS, MMSE ²	MRI ³	CMV Screen ⁴	CMP and CBC ⁵	Blood for immunologic monitoring and Sub-clinical Autoimmunity ⁶
Screening and Pre-enrollment	Prior to Consent	X	X	X		X	
Consent	Within 6 weeks of OR				X	X	
Leukapheresis ⁷	After Consent					X	X
RT/TMZ	Per SOC (starts within 6 weeks of OR)					X	
Post-RT TMZ cycle 1	Within 4 (±2) weeks of RT			X		X	
Basiliximab Infusion (Group III only)	Day 14 (± 2 days)		X			X	X
Td Booster IM	Day 20 (± 2 days) so long as before V#1						
Vaccine #1	Day 21 (± 2 days)		X				X
Basiliximab Infusion (Group III only)	Day 28 (± 2 days)		X			X	X
Vaccine #2	Day 35 (± 2 days)		X				
Vaccine #3	Day 49 (± 2 days)		X				
Leukapheresis	4 (± 2) weeks after V#3					X	X

¹ WHO Grade IV Glioma with definitive resection prior to enrollment, with residual radiographic contrast enhancement on most recent CT or MRI of <1 cm in maximal diameter in any axial plane.

² Clinical evaluations with each vaccine will include a general physical examination, complete neurologic examination, and KPS rating. MMSE will be performed at baseline only.

³ A baseline and study eligibility MRI (with and without gadolinium enhancement) of the brain per standard of care for comparison to subsequent MRI images will also be obtained. MRI or contrasted CT, every 8 ± 4 weeks per PRTBTC standard of care (may be adjusted by the treating neuro-oncologist).

⁴ A *CMV* immune screen will also need to be drawn at one of these clinic visits following consent and prior to initiation of vaccine therapy.

⁵ CMP and CBC (with auto differential) to confirm eligibility, and as per standard of care prior to and following surgery, and during SOC monthly and study cycles of TMZ and RT (if applicable).

⁶ Blood work for immunologic monitoring will be drawn before each leukapheresis (1 red top only prior to phereses), basiliximab (Group III), on the day of vaccine #1 (9 yellow/2 red top only at this visit), and then prior to each vaccine after vaccine #3 (9 yellow/2 red top tubes) and/or at progression (whichever comes first). For subjects who complete all 10 study vaccines without progressing, an attempt will be made to obtain blood for immunologic monitoring 2-3 times a year at standard Duke Preston Robert Tisch Brain Tumor Center visits and at progression (whichever comes first). Peripheral blood for immunologic immune monitoring will be placed in 9 yellow tops and 2 red top tubes for a total of about 90 mLs and delivered to the BTIP lab for processing. Plasma from the yellow top tubes will be collected at each time point listed where immunologic monitoring is done. 2 yellow and 1 red top tubes will be obtained at the pre-conditioning visit (all Groups) and at the SPEC/CT imaging visits (Groups I and II only). Blood work for sub-clinical autoimmunity will be drawn before basiliximab (Group III), or vaccine #1 (all other groups), and repeated only if clinically indicated. Laboratory evaluations to detect subclinical disease will be obtained as follows: serum thyroglobulin Ab (Lab Code 1802105), rheumatoid factor (Lab Code 5560195), antinuclear Ab (Lab Code 5560214), Thyroid Profile (Lab Code 1850277), and CMP (Lab Code 1004261). Total volume for sub-clinical autoimmune testing is < 20 mLs.

⁷ Initial leukapheresis will be scheduled following consent. Per standard Duke Apheresis Protocol, all subjects will have CBC, CMP, ionized Calcium, and βHCG within 48 hours prior to the procedure(s). Follow up leukapheresis will occur approximately 4 ± 2 weeks after third immunization to obtain PBMCs for Immunologic Monitoring and generation of additional DCs for continued vaccinations. Leukapheresis can be obtained up to every 2 weeks if needed according to the Duke Apheresis Center protocol, but these will likely be needed less than every 2 months throughout the study to generate enough DCs to continue vaccinations. Blood for immune monitoring will be drawn prior to each leukapheresis (1 red top tube – approximately 4 mLs).

Appointment	Time and Range	Tumor Pathology ¹	Physical and Neurologic Exam KPS, MMSE ²	MRI ³	CMV Screen ⁴	CMP and CBC ⁵	Blood for immunologic monitoring and Sub-clinical Autoimmunity ⁶
TMZ Cycle 2 (slight delay start)	To start following V#3		X	X		X	
Pre-conditioning ⁸	1 day before V#4		X			X	X
Vaccine # 4 ⁹ (¹¹¹ In-labeled DCs) (Groups I & II only)	Day 21(± 2 days) of second cycle of TMZ						X
Migration studies ¹⁰	1 day and 2 days after V#4						X
Vaccines with Cycles of TMZ ¹¹	On day 21 (± 2 days) of each cycle of TMZ		X	X		X	X
Monthly Vaccines After TMZ not to exceed 10	Every month (± 2 weeks)		X	X		X	X
Progression ¹²		X		X			X

12.3 End of Treatment

Vaccines are given as described above for a total of 10 or until progression (whichever comes first). Once the vaccinations are complete, the treatment phase of the study will be over and the follow-up period will begin.

If the patient is determined to have progressive disease, the patient may be considered for eligibility on the INTERCEPT study (INTracerebral EGFR-vIII Chimeric Antigen Receptor Gene-Modified T Cells for PaTients with Recurrent GBM, Pro00083828). If the patient is determined to be eligible for the INTERCEPT study (Pro00083828), the cells extracted from leukapheresis while they were on this study, ELEVATE, will be used to create the CAR T cells for administration in the INTERCEPT study.

12.4 Follow-up Period

Patients will be followed for survival, progression, and subsequent therapies only, and this data will be recorded by the research team. For recording of subsequent therapies, the type of therapy(ies) that the subject receives will be recorded with approximate start and stop date, if

⁸ On day before the fourth DC vaccine, patients will receive vaccine site pre-conditioning strategy (Group I-unpulsed DCs i.d.; Group II and III- Td i.d.). A single dose of Td toxoid (1 flocculation unit, Lf) or 1 x 10⁶ autologous unpulsed DCs will be administered to a single side of the groin 12-24 hours prior to the fourth DC vaccine, which is always given bilaterally at the groin site. Standard of care blood for CBC and CMP will be drawn during the pre-conditioning visit. 2 yellow and 1 red top tubes for immune monitoring will be obtained during the pre-conditioning visit.

⁹ At the day of the 4th vaccine (prior to administration), 9 yellow and 2 red top tubes obtained for immune monitoring. Patients in Groups I and II will then receive ¹¹¹In-labeled DCs to compare the effects of different skin preparations on DC migration followed by SPECT/CT imaging immediately.

¹⁰ SPECT/CT imaging will be performed at 1 and 2 days after injection of Vaccine #4 for patients in Groups I and II. At the SPECT/CT imaging visits 1 and 2 days after Vaccine #4, 2 yellow and 1 red top tubes for immune monitoring will be obtained only on patients randomized to Groups I and II (not Group III).

¹¹ Monthly cycles of TMZ will be initiated at the discretion of the treating neuro-oncologist according to pathology.

¹² As part of standard care for these patients, upon tumor progression, participants may undergo stereotactic biopsy or resection. As this is not a research procedure consent will be obtained separately. However, if tissue is obtained, it will be used to confirm tumor progression histologically and to assess immunologic cell infiltration and pp65 antigen escape at the tumor site.

possible. For subjects who complete all 10 study vaccines without progressing, an attempt will be made to obtain blood for immunologic monitoring 2-3 times a year at standard Duke Preston Robert Tisch Brain Tumor Center visits. If the subject progresses in the follow-up period, blood for immunological monitoring will be drawn at the time of progression, if possible.

12.5 End of Study

Rationale for taking a patient off study will be documented (see section 12.6.1). In the Follow-up Period, patients will be followed for survival, progression, and subsequent therapies only, and this data will be recorded by the research team.

12.6 Early Withdrawal of Subject(s)

12.6.1 Criteria for Early Withdrawal

Subjects may voluntarily withdraw from the study at any time. Subjects may be withdrawn by the PI and considered screen failures prior to vaccine therapy and the PI may also withdraw a subject from the study at any time based on his/her discretion. Reasons for PI-initiated withdrawal may include, but are not limited to the following:

- Inability to complete approximately 6 weeks of RT with TMZ as per standard of care.
- Inability to tolerate TMZ (either requiring a delay in cycles of TMZ, dose adjustment, or discontinuation).
- Patients with an active infection requiring treatment or having an unexplained febrile illness ($T_{max} > 99.5^{\circ} F$).
- Patients requiring an increase in corticosteroids, with the exception of nasal or inhaled steroid, such that at the time of first vaccination they require a dose above physiologic levels, will be removed from the study and replaced. For the purposes of this study, physiologic dose will be defined as < 2 mg of dexamethasone / day. Once vaccinations have been initiated, if patients subsequently require increased steroids, they will still be permitted to remain on the study, but every effort will be made to minimize steroid requirements.
- Adverse events
- Abnormal laboratory values
- Abnormal test procedure results (DCs fail to meet release criteria; inability to tolerate leukapheresis)
- Protocol deviation
- Administrative issues
- Disease progression
- Pregnancy

12.6.2 Follow-up Requirements for Early Withdrawal

Consented subjects that are withdrawn prior to randomization for any of the aforementioned reasons will be considered eligibility failures and thus will not be followed for survival. All other subjects will be followed by the study coordinator until death or are lost to follow-up.

Subjects that received **any** basiliximab (Group III only) or vaccine therapy will be assessed and followed or adverse event monitoring/safety analysis for at least 1 month following the last vaccine (or basiliximab infusion if in Group III).

12.6.3 Replacement of Early Withdrawal(s)

Subjects who voluntarily withdraw prematurely or who are withdrawn by the PI prior to randomization will be replaced.

12.7 Study Assessments

12.7.1 Medical History

Medical history will be obtained from the Duke electronic system and from the subject and/or family at the screening visit and reviewed at each study visit. This data may include the following:

- All past medical and surgical history
- Current medications
- Changes in physical or neurologic symptoms
- Any adverse events.
-

12.7.2 Physical Exam

Vital signs and physical and neurologic examinations will be assessed and recorded along with a KPS score prior to enrollment and at each visit. Curran Group Status will be performed at time of consent. Please see appendices – Section 18.2 for Curran Group Status Form.

12.7.3 Use of Antihistamines

Subjects will be advised to avoid antihistamine use 48 hours prior to each vaccine administration, the day of vaccine administration, and for 48 hours following each vaccine administration. If the subject has a pre-existing condition that requires antihistamine usage, the PI and the treating oncologist will decide if it is safe and appropriate for the subject's antihistamines to be held before and following vaccine administrations.

12.7.4 Radiologic Evaluations

Patients with newly-diagnosed GBM will be imaged by MRI as per standard of care for eligibility and baseline measurements, and to assess progression prior to vaccine therapy; although the purpose of this study is not to detect tumor responses, any evidence of tumor response will be determined according to the Duke PRTBTC SOP (see Appendices – Section 18.2). RANO criteria[127] will be used for overall assessment of tumor response and pseudoprogression. Pseudoprogression by the RANO response criteria is defined as follows: 1) $\geq 25\%$ increase in the sum of the products of perpendicular diameters of enhancing lesions compared with the smallest tumor measurement obtained either at baseline (if no decrease) or best response; 2) significant increase in T2/FLAIR non-enhancing lesion compared with baseline scan or best response after initiation of therapy - not caused by comorbid events (eg, radiation therapy, demyelination, ischemic injury, infection, seizures, postoperative changes, or other treatment effects); 3) any new lesion; clear clinical deterioration not attributable to other causes apart from the tumor (eg, seizures, medication adverse effects, complications of therapy, cerebrovascular events, infection, and so on); 4) failure to return for evaluation as a result of death or deteriorating condition. If pseudoprogression is suspected, the subject will continue with

vaccine therapy for a minimum of 2-3 subsequent months so long as subject remains clinically and radiographically stable compared to the MRI showing suspected pseudoprogression. If the subject continues to do well beyond the 3 months, they will continue on study as planned. Subjects demonstrating definitive progression will be removed from study. Tumor progression will need to be documented histologically, unless there are clinical contraindications, to exclude inflammatory responses presenting as radiographic or clinical changes, which could indicate potentially toxic or therapeutic responses and not tumor progression. If tissue is obtained through the Duke Brain Tumor Biorepository, it will be used to confirm tumor progression histologically and to assess immunologic cell infiltration and antigen escape using IHC. Upon progression, patients may be treated on other therapies as directed by the treating Oncologist.

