Effective March 2017 (AMD 49), randomization of patients to Group III has been terminated due to results from the related REGULATE study (IRB # Pro00000581), a study that evaluated the safety, toxicity, and efficacy of T Reg inhibition with basiliximab. REGULATE was used as the model for Group III in ELEVATE. Recent analyses of REGULATE data have shown that although the regulatory T cells were depleted, the cells did not show pp65 reactivity and their activation status was reduced. Patients previously randomized to Group III will continue on study as planned.

With AMD49, approximately 79 patients will ultimately be randomized to subsequent treatment after completion of radiation treatment with concurrent temozolomide, including 9 patients previously randomized to Group III. As originally planned, an interim analysis will be conducted after approximately 35 patients have been randomized to Groups I and II each in order to make a decision concerning the accrual of additional patients to address efficacy objectives within patient subgroups defined by CMV status (see Section 15.8).

All Groups

All patients will then be vaccinated in conjunction with subsequent TMZ cycles every 5 ± 1 weeks for a total of 6 to 12 cycles after RT at the discretion of the treating oncologist. DCs will be given on day 21 ± 2 days of each TMZ cycle. DC vaccinations will continue during TMZ cycles up to a total of 10 vaccines unless progression occurs. Patients will be imaged bimonthly at the discretion of the treating oncologist without receiving any other prescribed anti-tumor therapy. Patients will undergo an additional leukapheresis for generation of DCs if needed to continue vaccinations. As part of standard care for these patients, upon tumor progression, participants may undergo stereotactic biopsy or resection. As this is not a research procedure consent will be obtained separately. However, if tissue is obtained, it will be used to confirm

tumor progression histologically and to assess immunologic cell infiltration and pp65 antigen escape at the tumor site.

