9.1.4 Safety Considerations

Management of Toxicities

If a Grade 3 NCI CTC or greater toxicity is seen that is not attributable to a concomitant medication, co-morbid event, or disease progression that has been documented radiographically or clinically, the next immunization for that patient will be withheld for up to 2 months or until the NCI CTC toxicity improves to a Grade 2 or until the KPS score returns to within 10 points of baseline. However, planned procedures requiring hospitalization, or long-term clinical decline that is now seen in patients years from WBRT, which are clearly not related to study drug, but

are the natural development common in this patient population, will not be considered an unacceptable toxicity nor will have immunizations withheld.

Adverse Event Reporting and Documentation

An “Adverse Event” will be defined as any adverse change from the subject’s pre-treatment baseline condition (which is assessed at the post-RT/TMZ clinic visit), including any clinical or laboratory test abnormality that occurs during the course of research after the time of randomization. Adverse events will be categorized and graded in accordance with the NCI CTC (Version 4).

A “Serious Adverse Event” will be defined as an undesirable sign, symptom or medical condition which: 1) is fatal or life threatening; 2) requires inpatient hospitalization or a prolongation of existing hospitalization; 3) results in persistent or significant disability/incapacity; 4) constitutes a congenital anomaly or a birth defect and/or; 5) medically significant such that it may jeopardize the subject, and may require medical or surgical intervention to prevent one of the outcomes listed above.

A summary of all adverse events (not just those considered related to study drug) that occur following randomization will be kept which will categorize the event by organ system, relationship to treatment, its grade of severity, and resolution. Periodic review by the PI and monthly review at the PRTBTC Adverse Event meeting of the collective adverse events will occur with the intention of identifying any trends or patterns in toxicity. If any such trends are identified, depending on their severity and frequency, a protocol amendment will be considered.

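### Section 12.7.4 lists death and tumor-caused decline under pseudoprogression, and Section 15.6.1 censors PFS at last follow-up instead of last tumor assessment

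*Combined protocol and SAP*

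**What the plan says.** Table 1 makes median PFS from randomization the key secondary endpoint. Section 15.6.1 defines the event as progression or death and censors a patient alive without progression at the last follow-up.

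Section 12.7.4 adopts RANO for overall assessment, points to a response SOP (Section 18.2, uploaded separately), and then gives one list introduced by "Pseudoprogression by the RANO response criteria is defined as follows". After the imaging items, the list contains "clear clinical deterioration not attributable to other causes apart from the tumor" and "failure to return for evaluation as a result of death or deteriorating condition". Vaccination continues after suspected pseudoprogression "so long as subject remains clinically and radiographically stable compared to the MRI showing suspected pseudoprogression". Patients with definitive progression leave the study, but no separate list says what makes progression definitive.

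On imaging, Table 4 footnote 3 gives MRI or CT every 8 ± 4 weeks as standard of care, adjustable by the neuro-oncologist. Section 9.1 gives bimonthly imaging at the treating oncologist's discretion. Section 12.3 starts the follow-up period when vaccination is complete. Section 12.4 then follows survival, progression and later therapies. The only frequency it states is blood sampling 2-3 times a year.

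**The concern.** There are two separate weaknesses in how the key secondary endpoint is measured.

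- **Event definition.** The PFS event includes progression, yet the only list printed in the protocol carries the label of its opposite, apparent growth that is not progression. A person deriving PFS from the visible text could treat the same clinical decline as an event or as a non-event.
- **Censoring date.** PFS is known only up to the last time the tumor was assessed. If the censoring date is the last contact of any kind, months with a known vital status but no scan are counted as progression-free.

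Because the endpoint is a median, an error of this kind changes the reported result even when it is the same in every arm.

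**Working it through.** **Step 1: the label against the rest of the text.**

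- *Death.* A patient who did not return because of death cannot be stable compared with the suspicious MRI. Section 15.6.1 counts the death as failure. The conflict is direct.
- *Continuing decline.* This also cannot meet the stability condition. Section 15.6.1 does not define progression, so here it is silent, not contradictory.
- *Deterioration followed by a plateau.* Stability is judged against the MRI that raised the suspicion, so this patient could meet the condition. The conflict is weak.
- *Growth and new-lesion items.* These may be fair triggers for suspicion and are not disputed.

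**Step 2: size of the censoring effect.** The documents give no PFS sample size, power or significance level, so there is no planned figure to reproduce. What follows is an illustration.

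Inputs from the documents:
- PFS medians for scale: 4.4 months (pilot control arm, Section 7.3) and 10.4 months (time to progression in an earlier EGFRvIII vaccine study, Section 7.2.2).
- Vaccine #3 on Day 49, and vaccine #4 on day 21 of the next cycle: 49 + 21 = Day 70. Six further vaccines at 5-week cycles: 70 + 6 × 35 = Day 280, or T = 9.2 months. With 4- or 6-week cycles it is Day 238 or 322 (7.8 or 10.6 months). The start of the schedule is taken as randomization.

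Assumptions:
- Exponential times.
- Median survival after progression of 11.6 − 4.4 = 7.2 months (difference of the pilot control medians).
- A share u of patients has no imaging after T, so a later progression is first recorded at death.
- Follow-up uniform over 12-41 months (29 months of accrual plus 12).

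Event-free at T: exp(−ln 2 × 9.2/4.4) = 0.235, and exp(−ln 2 × 9.2/10.4) = 0.542.

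With λ = ln 2/median, μ = ln 2/7.2, s = t − T and S₀ the event-free share at T, PFS recorded as written is

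S(t) = S₀ × [(1 − u)e^(−λs) + u·h(s)], where h(s) = (μe^(−λs) − λe^(−μs))/(μ − λ).

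- *Median 4.4.* S₀ is already below 0.5, so the median is unchanged.
- *Median 10.4* (λ = 0.0666, μ = 0.0963). For u = 20% and s = 1.5: 0.542 × (0.8 × 0.905 + 0.2 × 0.993) = 0.500, so the median reads 10.7. For u = 40% and s = 1.93: 0.542 × (0.6 × 0.879 + 0.4 × 0.989) = 0.500, so it reads 11.1.
- *Cycle length.* At T = 7.8 (S₀ = 0.594) the same formula gives 11.0 and 11.8. At T = 10.6, S₀ = 0.494 and the median is unchanged.
- *18-month PFS with median 4.4* (s = 8.8, e^(−λs) = 0.250, h = 0.709). The true value is 0.235 × 0.250 = 0.059. Recorded: 0.235 × (0.8 × 0.250 + 0.2 × 0.709) = 0.080, and 0.235 × (0.6 × 0.250 + 0.4 × 0.709) = 0.102.

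**Step 3: last-assessment censoring.** Simulated under the same assumptions with T = 9.2, the 10.4-month median reads 10.5 (u = 20%) and 10.7 (u = 40%). The 18-month figure at a 4.4-month median reads 0.067 and 0.077. A small excess remains because an unseen progression followed by death is still dated at death.

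**Step 4: the test.** With 35 per arm, no true difference and equal u in both arms, a one-sided 0.15 log-rank test (the level set for survival, borrowed here) rejects in about 0.15 of simulated trials, the same as with complete imaging.

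**The case against.** The best defence is that 12.7.4 contains a labelling slip, and that the operative rules are in RANO and the SOP, which this review could not see. Much of that stands.

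- A reader might infer that the protocol has no progression criteria at all. The documents do not support this. They cite two sources that may hold the criteria, so the defect is that the visible text does not say which rule governs PFS.
- A reader might infer that deaths would be lost from PFS. They would not, because Section 15.6.1 counts death as failure whatever 12.7.4 calls it.
- A reader might infer that imaging stops after vaccination. Footnote 3 has no stated end, Section 9.1 says bimonthly, and Section 12.4 does follow progression. What can be said is narrower: those intervals are standard of care, adjustable or discretionary, and neither is stated to apply after vaccination ends.
- A reader might infer a biased comparison of arms. That needs the share of unassessed patients to differ between arms. Groups I and II are blinded to pre-conditioning and the documents give no reason for a difference. Group III is open, but has only 9 patients.
- The shares are assumed, and 10.4 months comes from a different vaccine study.

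The censoring rule itself remains. It is written in Section 15.6.1, and nothing elsewhere in the visible text limits last follow-up to the last tumor assessment.

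**Conclusion.** The point holds in a limited form. The pseudoprogression list conflicts with its own stability condition for death and continuing decline, and with Section 15.6.1 for death. The visible text leaves progression without criteria of its own.

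The censoring rule allows unassessed time to count as progression-free. On the central schedule, with 20-40% of patients unimaged after vaccine #10, the median moves by nothing at 4.4 months and by about 0.3-0.7 months at 10.4. Over the permitted cycle lengths the shift at 10.4 ranges from none to about 1.4 months. Late PFS at a 4.4-month median reads 8-10% instead of 6%. These figures rest on assumed shares, exponential times and a 7.2-month post-progression median.

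The effect falls on the reported PFS median and the tail of the curve. It does not fall on the log-rank test when shares are equal, or on overall survival. This should be corrected, but it does not threaten the key primary analysis.

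**What to change.** 1. For the PFS analysis, state in Section 15.6.1 which criteria define progression: either the 12.7.4 list relabelled, or a citation of RANO or the SOP. In that analysis, do not treat death or tumor-caused deterioration as pseudoprogression.
2. In Section 15.6.1, censor patients alive without progression at the last tumor assessment, and keep last-follow-up censoring as a sensitivity analysis. If the SOP already says this, cite it.
3. The sponsor should reconcile 12.7.4 with 9.1, 12.4, Table 4 footnote 3 and 15.6.1. No clinical rule is proposed here.

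The cost is wording plus deriving last-assessment dates from existing records, with no new visits. The downside is some follow-up time given up and a slightly shorter PFS median. On the central schedule above, the change is nil at 4.4 months and about 0.2-0.5 months at 10.4 (10.7 to 10.5, and 11.1 to about 10.7).
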